5.3.3.13 Other

Serum pregnancy tests post-baseline will be listed.

5.3.3.14 Hepatitis flares and HBsAg

Relationships between hepatitis flares and HBsAg loss (defined as at least two consecutive negative HBsAg results) will be evaluated by comparing the proportion of patients with HbsAg loss in patients with and without hepatitis flares through Day 169.

The proportion of patients with HbsAg loss through Day 169 will be analyzed using logistic regression models with treatment group as factor and hepatitis flares and ALT at baseline as covariates. The analysis of maximum likelihood and odds ratio estimates for patients predicting a 'Yes' in verifying HBsAg loss will be shown.

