3.2. Secondary Efficacy Endpoints

- Proportion of patients achieving serologic clearance of HBsAg on Day 169
- Proportion of patients achieving serologic clearance of HBV DNA on Day 169
- Changes in qHBsAg, HBV DNA, hepatitis B core-related antigen (HBcrAg) and pre-genomic RNA (pg-RNA) levels, Baseline to Days 85 and 169
- Change in IFN-γ frequency by ELISpot assay in PBMCs, Baseline to Days 85 and 169

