3.3. Exploratory Efficacy Endpoints

- Proportion of patients achieving serologic clearance of HBsAg on Day 505
- Proportion of patients achieving serologic clearance of HBV DNA on Day 505
- Proportion of patients with anti-HBsAg antibodies (anti-HBs) on Day 505
- Changes in qHBsAg, HBV DNA, HBcrAg, and pg-RNA levels, Baseline to Days 323 and 505
- Change in IFN-γ frequency by ELISpot assay in PBMCs, Baseline to Days 323 and 505

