4.6. Schedule of Events

The schedule for study activities is presented in Table 1 for the Screening and Treatment Periods and in Table 2 for the Follow-up Period.

 Table 1
 Schedule of Events – Screening and Treatment Periods

Schedule of Ever	Screening Period Treatment Period									
Study Day		Telephone Visit (if needed) ^a	Day 1	Day 8, 36	Day 29	Day 57	Day 85	Day 113	Day 141	Day 169 or ET ^b
Week (s)	-4 to -1		0	7 days after prior visit	4	8	12	16	20	24
Window (days)	_	Up to 3 working days before Day 1	_	±2 days	±2 days	±2 days	±2 days	±2days	±2 days	±2 days
Dose of study medication			1		2	3	4	5	6	
Visit may be conducted at home or work or in part as a telemedicine visit ^c				X						
Informed consent	X									
Eligibility criteria check	X	X	X							
Demographics	X									
Medical history	X									
Concomitant medications (including immunosuppressive medications, vaccines, and new HBV treatments) ^d	X	X	X	X	X	X	X	X	X	X
Complete PE	X									X
Targeted and symptom-driven PE	71		X	X	X	X	X	X	X	11
Height, weight, and BMI	X									X
Vital signs ^e	X		X	X	X	X	X	X	X	X
Fibroscan ^f	X									
ECG e	X									X
Urine pregnancy test ^g	X		X		X	X	X	X	X	X
Drug and alcohol screen	X									
Hepatitis B genotype h	X									
HCV, HDV, and HIV tests	X									
Safety labs °	X		X	X	X	X	X	X	X	X
Liver panel °	X		X	X	X	X	X	X	X	X
HBV serology and viral markers i	X		X				X			X
Whole blood for PBMC isolation			X				X			X
Randomization		Xª	X							
Study medication administration (number)			1		2 j,k,l	3 j,k,l	4 j,k,l	5 j,k,l	6 ^{j,k,l}	
Diary distribution (D) review (R) p			D	R	D	D	RD	RD	RD	R

Screening Period		Treatment Period								
Study Day	Day -35 to Day -4	Telephone Visit (if needed) ^a	Day 1	Day 8, 36	Day 29	Day 57	Day 85	Day 113	Day 141	Day 169 or ET ^b
AEs, including MAEs, NCIs and IMCs, and reactogenicity (systemic and local) ^m	X	X	X	X	X	X	X	X	X	X
Stored blood sample for future analyses ⁿ			X							X

AE = adverse event; BMI = body mass index; ECG = electrocardiogram; ET = early termination; HBV = hepatitis B virus; HCV = hepatitis C virus; HDV = hepatitis delta virus; HIV = human immunodeficiency virus; MAE = medically-attended adverse event; NCI = new-onset chronic illness; IMC = immune-mediated medical condition; PBMC = peripheral blood nonnuclear cell; PE = physical examination; UA = urinalysis

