- ^a Randomization may occur up to 3 working days before Day 1 (the day of first dosing) to allow for the possible preparation of study medication by a central pharmacy and shipment to the study site. If the patient is to be randomized before Day 1, the eligibility of the patient will be confirmed by a telephone visit prior to randomization. Concomitant medications AEs will also be assessed.
- b If a patient prematurely discontinues study medication before Day 169, Day 169/Early termination procedures will be performed. Patients who prematurely discontinue study medication will remain in the study for Follow-Up Period study assessments, the dates of visits adjusted to correspond to 13, 26, 39 and 52 weeks after the last dose of study medication.
- ^c A telemedicine visit would include a home visit by appropriate trained personnel to perform a target and symptom-driven physical and obtain vital signs and safety laboratories. The remaining portions of the visit may be conducted virtually by the study investigator.
- d After Day 169 or ET, only immunosuppressive medications, vaccines, and new HBV treatments or medications associated with MAEs, NCIs, SAEs, hepatitis flares, or hepatic injury will be recorded.
- ^e Measured before any blood sample collection.
- f Not required if performed within 12 months or if no fibrosis seen on liver biopsy within 2 years before screening.
- g For women of childbearing potential only. A serum pregnancy test will be obtained in lieu of a urine pregnancy test at screening.
- h Hepatitis B genotyping will be performed at screening if it has not been documented in the prior medical record.
- ¹ Serology and viral markers = HBsAg, anti-HBs, HBVDNA, pg-RNA, HBcAg, HBeAg, HBeAg antibody.
- Jif the patient has experienced an acute illness or temperature > 38°C in the 2 days prior to dosing, the administration of study medication and corresponding visit will be delayed until the illness or fever has resolved.
- k Investigators will review the eligibility of all patients to determine if the next treatment is to be administered. Eligibility for the next treatment will include 1) confirmation that patients did not meet a Stopping Rule (Section 7.1.1); 2) confirmation that the pre-treatment liver parameters are within acceptable ranges for treatment (Section 4.1); 3) confirmation that patients do not have a new confirmed or suspected IMC (Appendix 2). Patients not meeting these criteria will not be treated.

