4.2.2 Secondary Efficacy Endpoint

Proportion of patients achieving serologic clearance of HBsAg on Day 169

A patient is considered to have achieved serologic clearance of HBsAg on Day 169, if HBsAg on Day 169 is below the limit of quantitation (defined as 0.05 IU/mL).

Proportion of patients achieving serologic clearance of HBV DNA on Day 169

A patient is considered to have achieved serologic clearance of HBV DNA (PCR) on Day 169, if HBV DNA (PCR) on Day 169 is below the limit of quantitation (defined as 10 IU/mL).

Changes in qHBsAg, HBV DNA, HBcrAg and pg-RNA levels, Baseline to Days 85 and 169
 Changes in qHBsAg, HBV DNA, HBcrAg and pg-RNA levels from Baseline to Days 85 and 169
 are defined as:

Change of Test from Baseline to Day 85 = Test value [Day 85] – Test value [Baseline];

Change of Test from Baseline to Day 169 = Test value [Day 169] – Test value [Baseline];

where Test correspond to the following quantitative tests:

qHBsAg, HBV DNA and HBV DNA log, HBcrAg (Log U/mL and kU/mL) and pg-RNA

• Change in LPMIX9 IFN-γ Spot Forming Cells (SFC) by ELISpot assay in PBMCs, Baseline to Days 85 and 169

Change in LPMIX9 IFN-γ SFC by ELISpot assay in PBMCs, Baseline to Days 85 and 169 are defined as:

Change of LPMIX9 IFN-γ SFC from Baseline to Day 85 = LPMIX9 IFN-γ SFC [Day 85] – LPMIX9 IFN-γ SFC [Baseline];

Change of LPMIX9 IFN-γ SFC from Baseline to Day 169 = LPMIX9 IFN-γ SFC [Day 169] – LPMIX9 IFN-γ SFC [Baseline]

Where LPMIX9 is a pool of the 9 peptides contained in FP-02.2. Values for analyses are LPMIX9 raw values corrected with the control.

- Change in LPMIX9 IFN-γ Spot Forming Cells (SFC) by ELISpot assay in PBMCs:
 - Some replicates of some subjects and days, the -ve Control was higher than the analogous LPMIX9 value which led to negative values.
 - Given that the control does not correspond to the analogous LPMIX9 in each of the replicates since the corresponding wells are not linked, the calculation of the continuous parameter to be analyzed, will be revised as follows:
 - Mean (i=1,2,3) of ["Value for Peptide LPMIX9 (R#i)"] Mean (i=1,2,3) of ["-ve Control for Peptide LPMIX9 (R#i)"] where R#i is replicate #i, i=1,2,3
 - Adding a new specification: If the result turns out negative, it will round up to "0"

Please refer to section 5.3.2 for details on the handling of intercurrent events and missing data or all the secondary endpoints.

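### In the flare analysis (SAP 5.3.3.14), HBsAg clearance first seen at Day 169 cannot count as loss, because the rule needs two consecutive negatives and only Days 85 and 169 are sampled after baseline within the window

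*SAP*

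**What the plan says.** SAP 5.3.3.14 relates hepatitis flares to "HBsAg loss (defined as at least two consecutive negative HBsAg results". It compares the proportion with loss between patients with and without flares, and then states: "The proportion of patients with HbsAg loss through Day 169 will be analyzed using logistic regression models". It does not say how to score a first negative at Day 169, does not mention later confirmation, and does not tie the word negative to a numerical limit.

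SAP 4.2.2 counts a patient as having cleared HBsAg "if HBsAg on Day 169 is below the limit of quantitation (defined as 0.05 IU/mL". One value is enough. SAP 4.2.1 accepts the same single value as one of two routes to the primary response.

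The sampling schedule is in Protocol 4.6. In Table 1 the row "HBV serology and viral markers" is marked at Screening, Day 1, Day 85 and Day 169/ET. The footnote confirms that HBsAg is in that panel: "Serology and viral markers = HBsAg, anti-HBs, HBVDNA, pg-RNA, HBcAg, HBeAg, HBeAg antibody". The secondary endpoints match the schedule ("levels, Baseline to Days 85 and 169"). Table 2 adds Days 323 and 505, which serve the exploratory endpoints: "Changes in qHBsAg, HBV DNA, HBcrAg, and pg-RNA levels, Baseline to Days 323 and 505".

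Protocol 10.4.2 plans to examine flares against HBsAg loss and/or decline by logistic and linear regression. It contains no two-negatives rule.

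**The concern.** A rule that needs two consecutive negatives, applied to a window with two post-baseline samples, leaves no room for a patient who clears after the first of them. That patient appears as cleared in the clearance tables and as no loss in the flare tables, with nothing in the SAP to explain the difference.

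At stake is whether the analysis can answer the protocol's question. Flares are counted from ALT across the whole treatment period (SAP 4.3 and 5.3.3.8), while loss can be established only from negativity already present halfway through it. Protocol 1.4 and 4.5 extend dosing from 3 to 6 doses because immune responses rose with successive doses, so a later virologic effect is at least plausible under the design's own reasoning. SAP 5.3.3.14 carries forward only the loss part of the protocol's loss-and/or-decline question, so this one definition bears the whole analysis.

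**Working it through.** The plan states no figure for this analysis, so there is none to reproduce. The check is a count of samples and an enumeration of patterns.

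**1. Samples in the window.** Post-baseline HBsAg draws up to Day 169 (Protocol Table 1): Day 85 and Day 169, so 2. Possible consecutive post-baseline pairs: 2 − 1 = 1.

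**2. Early discontinuation adds no pair.** The ET visit takes the place of the Day 169 visit. Follow-up then has "the dates of visits adjusted to correspond to 13, 26, 39 and 52 weeks after the last dose of study medication", and Table 2 draws serology only at the second and fourth of these visits. The earliest case is a patient who stops after Dose 1: Day 1 + 26 × 7 = Day 183. With the 10-day window this is Day 173 at the earliest, still after Day 169. Only an unscheduled repeat test, which the documents do not provide for, could supply another negative.

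**3. Patterns, assuming clearance is sustained once seen.**

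| First negative at | Negative at Day 169 (SAP 4.2.2) | Two consecutive negatives by Day 169 (SAP 5.3.3.14) | Two consecutive negatives if Day 323 may confirm |
|---|---|---|---|
| Day 85 | yes | yes | yes |
| Day 169 | yes | **no** | yes |

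One edge case: 5.3.3.14 does not restrict the pair to post-baseline samples, so negatives at Day 1 and Day 85 would literally qualify. That would not be loss arising after baseline.

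**4. Flare timing.** Table 1 schedules liver panels at Days 1, 8, 29, 36, 57, 85, 113, 141 and 169. A counted post-baseline loss must already be negative at Day 85, the Dose 4 visit. A flare first detected at Day 113, 141 or 169 therefore cannot precede it. A flare at Day 113 followed by a first negative at Day 169 is entered as flare, no loss.

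**5. Share of clearances counted (assumption only).** The documents give no distribution of clearance times. Let u = (85 − 1)/(169 − 1) = 84/168 = 0.5 be the fraction of the window elapsed at Day 85. Among patients who clear between Day 1 and Day 169 and stay negative:
- uniform timing: u = 50% counted;
- late-weighted (density rising linearly): u² = 25% counted;
- early-weighted (density falling linearly): 1 − (1 − u)² = 75% counted.

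**6. Direction of any bias (assumption only).** Take true loss risks of 20% with a flare and 5% without: RR = 20/5 = 4.0 and OR = (0.20/0.80)/(0.05/0.95) = 4.75.
- Half missed in each group: 10% and 2.5%. RR = 4.0; OR = (0.10/0.90)/(0.025/0.975) = 4.33.
- 75% missed with a flare, 25% without: 5% and 3.75%. RR = 1.33.
- 25% missed with a flare, 75% without: 15% and 1.25%. RR = 12.

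The association can be nearly unchanged, weakened or strengthened, depending on timing that the documents do not describe.

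**The case against.** Confirmed loss is a legitimate endpoint. SAP 4.2.2 speaks of clearance on one day and 5.3.3.14 of loss; a point-in-time and a confirmed endpoint can coexist. Protocol 4.4 itself cites variability in the quantitative HBsAg assay, which is a reason to want confirmation. A single-negative rule gives up specificity, and false positives weaken an association between rare events. With the same assumed risks and 98% specificity, the observed risks are 0.20 + 0.80 × 0.02 = 21.6% and 0.05 + 0.95 × 0.02 = 6.9%, so RR falls from 4.0 to about 3.1. All of this stands, and it is why the two-negatives version should be kept. It does not repair the window, which cannot confirm a negative first seen on its last day.

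A reader might infer that the rule biases the comparison toward no relation. The documents do not support that. Late clearers are dropped with and without flares alike, and step 6 of the working shows that attenuation needs late clearance to be relatively more common among flare patients. A reader might also infer that a first negative at Day 169 is misclassified. That presumes a single negative is true loss, which is not established.

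The analysis is also modest in rank. It sits in the safety section of a study that SAP 5.3 calls exploratory, and its tables are not flagged as top-line. Version 2.0 of the SAP postdates the Week 24 result, and the addendum's list of supplementary outputs does not include these tables. These facts limit the priority and require a post hoc label; they do not remove the inconsistency.

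**Conclusion.** The point holds on the schedule alone. Setting aside the Day 1 plus Day 85 edge case, loss through Day 169 is confined to patients already negative at Day 85. Clearance first seen at Day 169 is scored as no loss although the patient is a responder under SAP 4.2.1 and 4.2.2, and flares first detected from Day 113 on cannot be related to later clearance.

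The certain effect is lost events and lost precision. A reader might infer that most events are lost, but that is unproven: the 25% to 75% range rests entirely on assumed timings and sustained clearance. SAP section 2 reports that the primary and secondary endpoints were not met, so there may be few clearances, or none, to reclassify. Nor is it right that HBsAg is never sampled after Day 169. Days 323 and 505 are scheduled, but 5.3.3.14 does not use them.

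This is a weakness in a supportive analysis that is worth correcting. The primary and secondary results are untouched.

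**What to change.** In SAP 5.3.3.14, add an analysis of loss under the 4.2.2 definition (a single Day 169 HBsAg below 0.05 IU/mL), together with the missing-data rule of 5.3.2.2.1, so that it agrees with the reported clearance endpoint. Report it beside the two-consecutive-negatives version, and let Day 323 confirm a first negative at Day 169 where that sample was accrued. State how unconfirmed cases are scored, tie the word negative to the 0.05 IU/mL limit, and say whether pre-dose samples may form part of a pair. Label the addition post hoc, because the Week 24 interim has been reported.

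The cost is a short SAP amendment and a rerun of Tables 14.3.6.2 and 14.3.6.3; no new data are needed. There are two downsides. The single-negative version is unconfirmed and so less specific, and Day 323 confirmation will be incomplete because the study was terminated early.

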5.3.8 Data Handling Conventions and Transformations

For HBV serology parameters and viral markers that are continuous in nature as well as HBV pregenomic RNA, the following lower limit of quantitation (LLOQ) have been identified:

Test	LLOQ
HbsAg (IU/mL)	0.05
anti-HBs (mIU/mL)	5.00
quantitative HBV DNA(IU/ml)	10
HbcrAg (Log U/mL)	3
HbcrAg (kU/mL)	1
pg-RNA (log U/mL)	0.49

Also, some of the laboratory parameters could be reported in the form "< x" being "x" the LLOQ for that parameter.

For analyses, the values assigned to the lower limit of quantitation will be imputed as follows:

A value that is 1 unit less than the LLOQ will be used in statistical analyses if the datum is reported in the form of "< x" (where x is considered the LLOQ). For example, if the values are reported as < 50 and < 5.0, values of 49 and 4.9, respectively, will be used in statistical analyses.

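### The below-LLOQ rule in SAP 5.3.8 depends on printed decimals and gives one HBcrAg sample two different values, by an amount that depends on the unstated laboratory report format

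*SAP*

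**What the plan says.** SAP 5.3.8 lists a lower limit of quantitation (LLOQ) for each marker: HBsAg 0.05 IU/mL, anti-HBs 5.00 mIU/mL, HBV DNA 10 IU/mL, HBcrAg 3 log U/mL and also 1 kU/mL, and pg-RNA 0.49 log U/mL. There is no row for HBV DNA on the log scale. The rule for a result given as less than x is "A value that is 1 unit less than the LLOQ will be used in statistical analyses", with this example: "if the values are reported as < 50 and < 5.0, values of 49 and 4.9, respectively".

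The imputed values feed a secondary endpoint. Protocol 3.2 names "Changes in qHBsAg, HBV DNA, hepatitis B core-related antigen (HBcrAg) and pre-genomic RNA (pg-RNA) levels, Baseline to Days 85 and 169". SAP 4.2.2 applies it to "qHBsAg, HBV DNA and HBV DNA log, HBcrAg (Log U/mL and kU/mL) and pg-RNA" and defines change as a plain difference: "Change of Test from Baseline to Day 169 = Test value [Day 169] – Test value [Baseline]". SAP 5.3.2.2.3 summarises HBcrAg change in both units and fits a mixed model for repeated measures (MMRM) to HBcrAg, with the baseline value as covariate. It allows transformations where needed. The model text does not say which HBcrAg unit is used.

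No other section fixes the number of reported decimals, links the two HBcrAg units, or plans a sensitivity analysis for values below the limit. Protocol 10.6 leaves data handling conventions to the SAP, and Protocol 8.2.2 leaves virology methods to the laboratory manual.

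**The concern.** A substitution for a censored value is always a convention, but it should depend on the assay limit and give one concentration per sample. This rule does neither. The same sample takes a different value according to how many decimals the report carries, and the two HBcrAg scales need not describe the same concentration.

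At stake is the HBcrAg change endpoint. A patient who drifts just below the limit could enter the analysis with a tenfold fall, and one who drifts just above it with a tenfold rise. Imputed baselines also enter the model as covariate values.

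**Working it through.** **The rule as a formula.** If `<x` is printed with d decimals, the imputed value is x - 10^(-d). This reproduces the SAP's example: 50 - 1 = 49 and 5.0 - 0.1 = 4.9. Subtracting a literal 1 does not: 5.0 - 1 = 4.0, and HBsAg would become 0.05 - 1 = -0.95 IU/mL. The unit is therefore the last printed digit.

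**Same limit, two values.** 3 log U/mL = 10^3 U/mL = 1 kU/mL, so the two HBcrAg rows state one limit. With the limits as printed:

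- log scale: 3 - 1 = 2 log U/mL = 100 U/mL = 0.1 kU/mL
- linear scale: 1 - 1 = 0 kU/mL, whose logarithm is undefined

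**Dependence on format.** The documents do not give the report format, so zero, one and two decimals were tried on each scale.

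| Log report | Imputed log U/mL | Same in kU/mL | Change from 3.0 log |
|---|---|---|---|
| `<3` | 2 | 0.100 | -1.0 |
| `<3.0` | 2.9 | 0.794 | -0.1 |
| `<3.00` | 2.99 | 0.977 | -0.01 |

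On the linear scale, `<1`, `<1.0` and `<1.00` give 0, 0.9 and 0.99 kU/mL. None of these equals 0.100, 0.794 or 0.977, so the scales disagree in all nine combinations, although the gap is small when both carry two decimals.

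**Other markers.** The distance on the log10 scale from the limit to the imputed value is:

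- HBsAg, 0.05 to 0.04: ratio 0.80, about 0.10 log
- HBV DNA, 10 to 9: ratio 0.90, about 0.05 log
- pg-RNA, 0.49 to 0.48 log: 0.01 log

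For HBV DNA log, log10(9) = 0.95. If the rule were instead applied to a log report of `<1`, the value would be 0.

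**Effect on an arm mean.** Assume 40 patients per arm (SAP 5.1), all contributing, and k more patients in one arm crossing from 3.0 log to below the limit. The shift in that arm's simple mean is -(k/40) × step. The values of k are assumptions, and this is not an MMRM estimate.

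| k | `<3` (step 1.0) | `<3.0` (step 0.1) |
|---|---|---|
| 2 | -0.05 | -0.005 |
| 4 | -0.10 | -0.01 |
| 8 | -0.20 | -0.02 |

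For variance, one such patient has a squared change of 1.0² = 1.00 with `<3` and 0.1² = 0.01 with `<3.0`. A patient below the limit at both visits scores zero change in either format.

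**The case against.** The rule acts on the reported result, not on the LLOQ table, and the report format is not in the documents. If HBcrAg results carry one decimal, a censored result may read `<3.0`, and the step is then only 0.1 log. This stands: the full 1-log step is conditional. The SAP table prints 3 without a decimal while keeping decimals for other markers (5.00, 0.05, 0.49), so `<3` is plausible but not established.

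A reader might infer that all four markers suffer 1-log artefacts. The steps above do not support that. HBsAg, HBV DNA and pg-RNA move by 0.1 log or less, provided HBV DNA log comes from the imputed linear value.

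A reader might also infer that the rule manufactures a difference between arms. It is the same in both arms, so equal crossing rates give no expected difference, only distorted means and variance. Unequal rates are magnified, not created. Nor do the documents show how many patients lie near the HBcrAg limit, so a frequent effect cannot be claimed.

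The zero in kU/mL matters less than it might seem, because HBcrAg is also analysed in log units. It still blocks a plain log transformation of the kU/mL variable, and the two summaries still describe the same samples inconsistently.

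**Conclusion.** The point holds for HBcrAg. The stated rule gives contradictory values for one sample, and nothing in either document reconciles them. That conclusion needs no outside data.

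The size is conditional: -1.0 log for a patient moving from 3.0 log to below the limit if the laboratory reports `<3`, and -0.1 log if it reports `<3.0`. The effect on the treatment comparison depends further on unequal crossing rates, for which the documents give no figures.

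The primary endpoint is unaffected, because SAP 4.2.1 already counts HBsAg below 0.05 IU/mL as clearance whatever value is substituted. SAP Section 2 records that the Week 24 analysis did not meet the primary and secondary endpoints. A reader might infer that this rule influenced that result, but the documents contain no HBcrAg data that would show it. This is a flaw worth correcting in one secondary marker of an exploratory Phase 2 study.

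**What to change.** Replace the HBcrAg part of SAP 5.3.8 with one substitution on one scale, whatever decimals are printed, and obtain the other unit by conversion. For example, assign 0.5 kU/mL to any result below 1 kU/mL (3 log U/mL); then log10(500) = 2.70 log U/mL, and the move from 3.0 log to below the limit scores -0.30. The fraction is a convention and should be labelled as one. Likewise, derive HBV DNA log from the imputed linear value (9 IU/mL gives 0.95). State the laboratory's report format.

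A uniform half-LLOQ rule for every marker is not required. It would widen the step to 0.30 log for HBsAg, HBV DNA and pg-RNA, from about 0.10, 0.05 and 0.01.

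The cost is a small programming change and a rerun of the HBcrAg rows of Tables 14.2.2.3.1 and 14.2.2.3.2, plus HBV DNA log if its derivation changes. Since the results are already known, present the rerun beside the planned analysis, labelled as a corrected or sensitivity analysis.
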